3.3 POWER AND SAMPLE SIZE

The power to detect differences in the AUC of the LROC curve for the proposed statistical analysis using the current design baseline, i.e. 300 cases, each corresponding image read by 10 readers, was assessed through a simulation study. Specifically, the model outlined above was used to simulate 500 datasets across a range of effect sizes, where power was defined as the

proportion of datasets that yielded a significant p-value for testing the fixed effect of modality. The method of Dorfman, Berbaum and Metz, 1992 (DBM) was implemented utilizing statistical mixed model theory with jackknife estimates.

These simulations required assumptions regarding the magnitude of the variance components associated with the different random effects. As a pilot study to obtain estimates of variance components was not conducted, variance component estimates from Riverain study SoftView 510(k) (Record # BSSI-PR-09-00006) that uses a similar technology as the proposed ClearRead CT Insight device were used in all power simulations. Please note that the variance components listed in Table V were scaled by the total variance to represent the proportion of total variance explained by each component. All power estimates are dependent upon the appropriateness of the assumed variance components.

Table V: Variance component estimates from previous Softview reader study

Variance Component	Scaled Estimate
Reader (σ_{reader}^2)	0.0003
Case (σ_{case}^2)	0.1258
Modality-by-reader ($\sigma_{mod*reader}^2$)	3.8981E-05
Modality-by-case ($\sigma_{mod*case}^2$)	0.0257
Reader-by-case ($\sigma_{reader*case}^2$)	0.0127
Residual (σ_{res}^2)	0.8355

The mean difference $\Delta\mu = \mu_1 - \mu_2$ between modalities corresponding to a specified effect size γ was then calculated as

$$\Delta\mu = \gamma * \sigma_{res}.$$

Effect sizes of 0, 0.2, 0.5, and 1 representing no effect, a small, a moderate, and a strong effect respectively, were evaluated in this simulation study with the following rationale:

- a) An effect size of 0 was chosen to assess type I error in this study.
- b) An effect size of 0.1 was chosen to correspond to a change in AUC of LROC of 0.084, which is $0.10 \times \sqrt{0.8355}$.
- c) An effect size of 0.2 was chosen to simulate the expected small improvement in accuracy in time.
- d) An effect size of 0.5 was chosen to simulate the expected moderate improvement in accuracy or time.

Table VI presents a summary of the power simulations along with additional scenarios with fewer cases with 8 or 10 readers. Superiority is assessed as the proportion of simulations in which the upper bound of the confidence interval on the AUC difference is less than zero. The other power assessment is on the statistical significance of the difference between modality.

Table VI: Power estimates for superiority and statistically significant modality effect using previous Softview reader study to estimate variance components

			Power	
Number of Cases	Number of Readers	Effect Size	Superiority	Modality Effect
300	10	0	0.086	0.082
		0.05	0.606	0.490
		0.1	0.978	0.974
		0.2	1.0	1.0
		0.5	1.0	1.0
270	10	0	0.060	0.060
		0.2	1.0	1.0
		0.5	1.0	1.0
270	8	0	0.058	0.080
		0.1	0.932	0.878
		0.2	1.0	1.0
		0.5	1.0	1.0

The results show that the type I error is approximately controlled at the nominal level, i.e. 0.05, and therefore type I error is maintained at the desired level. Furthermore, the power to detect a change in AUC of at least 10% of the standard deviation is over 80% given the assumed magnitude of the variance components, even with only 270 cases and 8 readers.

Based on data from the literature referenced earlier in this report, potential variability and effect size for sensitivity can be assessed. Based on a mean difference in sensitivity of 0.0914 with overall standard deviation over all estimates of 0.1234 for an effect size of $0.0914/0.1234$, or 0.741, the superiority of ClearRead CT Insight would be detected with adequate power.

There are several scenarios including reduced number of cases and a reduced number of readers. Even with 270 cases and only 8 readers, the power of the study should be sufficient to detect an effect size of 0.1.

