3.2 STATISTICAL ANALYSES

Accuracy

To evaluate the hypothesis of superiority in terms of improvement in accuracy for ClearRead CT Insight vs. unaided, a mixed effects model (DBM) will be implemented (similar to the model outlined in Dorfman, Berbaum and Metz, 1997), where variance components will be included to account for reader, case, reader by case, reader by modality, case by modality and reader by case by modality. However, it is anticipated that the three-way interaction will be inestimable and will subsequently be dropped from the statistical model. Specifically, the hypothesis to test for superiority of ClearRead CT Insight vs. unaided is:

$$H_0: AUC_{\text{unaided}} - AUC_{\text{ClearRead CT Insight}} \geq 0.0 \text{ vs. } H_A: AUC_{\text{unaided}} - AUC_{\text{ClearRead CT Insight}} < 0$$

The AUC of the LROC is the primary endpoint to evaluate accuracy and the test of interest will be a two-sided 95% confidence interval on the effect of modality (i.e. *ClearRead CT Insight minus unaided*). Significance will be concluded if the upper bound of the two-sided 95% confidence interval does not include zero. If the null hypothesis (H_0) is rejected, the alternative hypothesis (H_A) is accepted and the superiority of using the ClearRead CT Insight system will be established.

Time

The second co-primary objective is to evaluate reduction in time spent per image for *ClearRead CT Insight vs. unaided*. Specifically, the hypothesis to test for superiority of *ClearRead CT Insight vs. unaided* is:

$$\mathbf{H_0 = T_{unaided} - T_{ClearRead CT Insight} \leq 0 \text{ vs. } \mathbf{H_A = T_{unaided} - T_{ClearRead CT Insight} > 0}$$

To evaluate the hypothesis of non-inferiority in terms of improved read time for *ClearRead CT Insight vs. unaided*, a mixed effects model will be implemented (similar to the model outlined in Dorfman, Berbaum and Metz, 1992), where variance components will be included to account for reader, case, reader by case, reader by modality, case by modality and reader by case by modality. However, it is anticipated that the three-way interaction will be inestimable and will subsequently be dropped from the statistical model.

The read times will be tested using a two-sided 95% confidence interval on the effect of modality (i.e. *ClearRead minus unaided*). Significance will be concluded if the upper bound of the two-sided 95% confidence interval does not include zero.

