With either analysis, the use of the mixed model could be modified to employ a bootstrap sampling approach if the model assumptions of the DBM method have been violated. The upper 95 % confidence limit for the difference in the areas under the curves would be calculated using 10,000 bootstraps in the MultiReader MultiCase (MRMC) ROC method.

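### Table VI does not support the claim that type I error is maintained, and its power at small effects fits neither the planned test nor the Table V inputs

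*Combined protocol and SAP*

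**What the plan says.** Section 3.2 (Accuracy) plans a mixed model with reader, case and all two-way terms, including case by modality. It states that "the test of interest will be a two-sided 95% confidence interval on the effect of modality", and adds: "Significance will be concluded if the upper bound of the two-sided 95% confidence interval does not include zero". The bootstrap alternative at the end of section 3.2 refers instead to "The upper 95 % confidence limit for the difference in the areas under the curves".

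Section 3.3 says that this model "was used to simulate 500 datasets across a range of effect sizes", using the Table V variance components and a mean difference equal to the effect size times the residual SD. Power is the "proportion of datasets that yielded a significant p-value for testing the fixed effect of modality". Table VI has a second criterion, Superiority, met when "the upper bound of the confidence interval on the AUC difference is less than zero". No confidence level is given for that interval.

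The text under Table VI draws two conclusions. On error control: "The results show that the type I error is approximately controlled at the nominal level, i.e. 0.05, and therefore type I error is maintained". On power, even with 270 cases and 8 readers: "the power to detect a change in AUC of at least 10% of the standard deviation is over 80" per cent.

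**The concern.** Table VI is the plan's only quantitative evidence on error control and power for the primary AUC endpoint. Three things in it do not fit the text.

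- The null rows for the planned design lie well above 0.05, yet the text says the level is held.
- Superiority, the stricter criterion under the planned interval, is met more often than Modality Effect.
- The power figures look high for the Table V inputs.

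An inflated null rate in a simulation said to use the planned model has two possible sources: the simulation code is wrong, or the planned analysis is anti-conservative. The documents do not say which. If the simulated error term carried over into the final analysis, the superiority claim itself would be affected.

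**Working it through.** **1. Null rates.** Section 3.3 gives 500 datasets. I read this as 500 per row, and every Table VI entry is a multiple of 1/500. For a binomial count with n = 500 and p = 0.05, the central 95% range is 0.032 to 0.070.

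| Design | Column | Rate | Count | P(this or more, if 0.05) | Exact 95% CI |
|---|---|---|---|---|---|
| 300 × 10 | Superiority | 0.086 | 43 | 0.0005 | 0.063–0.114 |
| 300 × 10 | Modality Effect | 0.082 | 41 | 0.0015 | 0.059–0.110 |
| 270 × 8 | Modality Effect | 0.080 | 40 | 0.003 | 0.058–0.107 |

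The other three null cells (0.060, 0.060, 0.058) are compatible with 0.05. Bonferroni over all six cells leaves the first at 6 × 0.0005 = 0.003. Pooled over its three null rows, Modality Effect is (41 + 30 + 40)/1500 = 111/1500 = 0.074 (CI 0.061–0.088, P = 0.00004). Superiority is (43 + 30 + 29)/1500 = 102/1500 = 0.068 (P = 0.001). Modality Effect is the p-value test, so its result does not depend on the confidence level behind Superiority.

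**2. Which test was simulated.** If the upper bound of a two-sided 95% interval is below zero, the two-sided p-value is below 0.05. With the same datasets, standard error and degrees of freedom, Superiority therefore cannot exceed Modality Effect, and its null rate should be 0.025. Table VI has 0.606 against 0.490, 0.978 against 0.974 and 0.932 against 0.878, and 0.086 against 0.082 under the null. All three Superiority null rates exceed 0.025 (the smallest, 0.058, has P = 0.00003). The ordering fits a one-sided 5% bound. Converting Superiority from one-sided 5% to two-sided 5% gives 0.48, 0.955 and 0.88, near the Modality Effect entries of 0.490, 0.974 and 0.878.

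**3. Power from Table V.** Inputs are modality-by-reader 0.000038981, modality-by-case 0.0257 and residual 0.8355. For R readers and C cases, fully crossed:

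SE = √[2 × (σ²mod×reader/R + σ²mod×case/C + σ²res/(R × C))]

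- 300 × 10: √[2 × (0.0000039 + 0.0000857 + 0.0002785)] = 0.0271
- 270 × 8: √[2 × (0.0000049 + 0.0000952 + 0.0003868)] = 0.0312

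By the section 3.3 formula, Δ = γ × √0.8355, which is 0.0457 at γ = 0.05 and 0.0914 at γ = 0.1. Treating the variances as known, the most favourable case, power is Φ(Δ/SE − 1.96) two-sided and Φ(Δ/SE − 1.645) for a one-sided 5% bound. The ratios Δ/SE are 1.684, 3.369 and 2.929. The column for estimated variances uses 200,000 draws of the mean squares, with Satterthwaite or Hillis degrees of freedom.

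| Scenario | Two-sided, known variance | Two-sided, estimated variance | Table VI Modality Effect | One-sided 5%, known variance | Table VI Superiority |
|---|---|---|---|---|---|
| 300 × 10, γ = 0.05 | 0.392 | 0.35 | 0.490 | 0.516 | 0.606 |
| 300 × 10, γ = 0.1 | 0.921 | 0.88 | 0.974 | 0.958 | 0.978 |
| 270 × 8, γ = 0.1 | 0.834 | 0.75–0.76 | 0.878 | 0.900 | 0.932 |

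Against the known-variance maxima, the Modality Effect counts have P = 0.000005, 0.0000004 and 0.004. The Superiority counts, read as one-sided 5%, have P = 0.00003, 0.01 and 0.009.

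The full error term holds its level in the same draws at 300 × 10: 0.025–0.026 directional and 0.050–0.052 two-sided.

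**4. A possible cause.** Leaving modality-by-case variance in the data but out of the error term reproduces most cells, including the raised null rates at 300 × 10 and 270 × 8. It does not fit the 270 × 10 null (0.060 stated, 0.088 expected) or 0.974 at 300 × 10 (about 0.95 expected). It is an inference from the numbers and is not stated in the plan.

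**The case against.** The strongest reply is that nothing here invalidates the trial. The section 3.2 model contains case by modality and holds its level on the Table V inputs. The planned 300 × 10 design keeps more than 80% power at effect size 0.1. The rows at 0.2 and 0.5 are not in dispute. Only a reduced scenario, 270 × 8, has its power claim put at risk. All of this stands, and it confines the defect to the planning table and its text.

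The plan says approximately controlled, half of the null cells pass, and the two 300 × 10 cells presumably share the same datasets. These are fair cautions. They do not rescue the sentence: it goes on to say the level is maintained, the failing cells are those of the planned design, and each is incompatible with 0.05 on its own.

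The test mismatch depends on section 3.3 meaning the section 3.2 interval. A one-sided 5% bound would explain the ordering of the columns. The complaint would then be that Table VI reports a more lenient test than the one planned, which still needs correcting.

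Finally, scaling Δ by the total SD (1.0 after scaling) instead of the residual SD gives two-sided power of 0.453, 0.958 and 0.893, and one-sided 5% power of 0.578, 0.979 and 0.941. These are roughly within the Monte Carlo error of 500 runs. That reading may explain the power gap. However, it contradicts the formula printed in section 3.3, assumes known variances and cannot affect the null rows.

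**Conclusion.** The concern holds: the type I statement is wrong as written. The planned design shows null rates of 0.086 and 0.082 where 0.032 to 0.070 is expected.

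The Superiority column appears to come from a more lenient test than the planned one. On the plan's own inputs, two-sided power is 0.35–0.39 and 0.88–0.92 at 300 × 10 (effect sizes 0.05 and 0.1), and 0.75–0.83 at 270 × 8 (effect size 0.1). The last range straddles the 80% that the text says is exceeded.

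This applies to the null, 0.05 and 0.1 rows only. It assumes 500 datasets per row, a fully crossed design, the Table V components and Δ = γ × residual SD. The argument about column ordering also assumes that both columns use the same datasets, standard error and degrees of freedom. The cause of the discrepancy cannot be settled from the documents.

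**What to change.** - Rerun Table VI with the exact final-analysis rule, and state that rule once, identically in section 3.2 (including the bootstrap paragraph) and section 3.3. For example: *Superiority is concluded if the upper bound of the two-sided 95% confidence interval for AUC(unaided) minus AUC(ClearRead CT Insight) is below 0.* The direction needs stating because section 3.2 currently defines the effect as ClearRead minus unaided. For that contrast an upper bound below zero would show a lower AUC with the device.
- Use an error term that includes modality-by-reader and modality-by-case variance, name the degrees-of-freedom method (Hillis is one suitable choice), and state that the final analysis uses the same error term.
- Use enough replicates to separate 2.5% from 5%. With 10,000, a true 2.5% gives about 0.022 to 0.028.
- Replace the Superiority column, report null rates against 2.5% directional and 5% two-sided, and restate power for 300 × 10 and 270 × 8.
- Delete the type I sentence unless the rerun supports it.

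The cost is a few hours of simulation and revised text. Stated power becomes less favourable and the 270 × 8 statement may have to be softened. The sample size does not change.
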